
Genotyping: In **SubAim 1c**, we will test the validity of our Cho score and isotope dilution measures by asking whether people with genetic polymorphisms known to increase risk for developing Cho deficiency-induced organ dysfunction have values for Cho score and isotope dilution that show that they have smaller pool size for any given diet treatment (and perhaps have altered choline biomarkers). For example, as discussed earlier about half of premenopausal women with a common PEMT SNP do not induce the gene and make less Cho and Intervention protocol template_18Dec2018

therefore must eat Cho. Based on our previous studies, we expect that 56% of premenopausal women will attenuate the rate at which they deplete of Cho because they can induce PEMT activity with estrogen (44% cannot due to *PEMT* SNPs), and we expect them to show will show intermediate changes in Cho pool size and thus, in the biomarkers. For the *PEMT* rs12325817-C SNP we genotype using RT-PCR (56) (it is in a region of Alu repeats that makes the genotyping array fail for this SNP). *PEMT* rs4646343-A and rs3760188-A are obtained with the array below.

In an exploratory study, we will ask whether other SNPs that create inefficiencies in choline metabolism also are associated with decreased choline pools size and alter choline biomarkers. We will use a custom Illumina Expanded Multi-Ethnic genotyping array (Mega-EX). This chip contains >2 million markers plus 899 added SNPs in genes of Cho and 1-carbon metabolism that were selected based on our published identification of SNPs (24, 25, 52, 55, 56) that altered Cho status. We will assess genotype cluster calls for accuracy, using Illumina's included sample-dependent and independent controls for assay performance, and replica samples will be included with every set of ~95 samples to assess allele calling consistencies. Poorly-performing DNA samples, markers that deviate from HWE ($P < 0.0001$) or have >5% assay failure, will be removed. Genotypic data will be stored as comma delimited text files and integrated into the database at UNC-NRI, where subsets are retrieved for analyses using established scripts. Haplotypes and frequency estimates for them will be obtained with a maximum likelihood method that accounts for pedigree structure using Sequential Oligogenic Linkage Analysis Routines (SOLAR) software (99). CNVs will be assessed as previously described (100).

5.2 Pharmacokinetic Evaluation: N/A.

5.3 Safety Evaluations:

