6.2 Secondary Endpoint

SubAim 1c: Determine whether people with genetic polymorphisms known to increase risk for developing choline deficiency-induced organ dysfunction are also more likely to have a worse choline status score and a reduction in choline pool size assessed using isotope dilution. A number of SNPs in genes of choline and folate metabolism have been associated with increased risk for developing organ dysfunction on a low choline diet. We hypothesize that people with these SNPs have a lower choline pool size/worse choline status score for any given choline dietary intake than do people without these SNPs.

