score will be calculated based on the OPLS weights and the variability explained in OPLS-R. Biomarkers with $VIP > 1.5$ will be considered the most important biomarkers responsible for prediction. Pathway analysis will be performed using GeneGo metacore (Thomson Reuters, <https://portal.genego.com>) and QIAGEN's Ingenuity Pathway Analysis (IPA®, QIAGEN Redwood City, www.qiagen.com/ingenuity).

Statistical methods (SubAim 1c). Linear model with repeated measures will be used to identify SNPs that increase (or decrease) the risk for developing choline deficiency-induced organ dysfunction. This analysis will be performed for each diet period (healthy men, pre- and postmenopausal women) separately. In each linear model, the choline status score defined by Aim 1 is the response variable. Diet effect (fixed), genotype effect (fixed), subject effect (random) and diet \times genotype interaction effect are the independent variables. In the repeated measures design, each subject serves as his/her own control. Therefore, confounding effect from genotype is not our concern. However, it is possible that genotype serves as a moderator, which interacts with the diet effect, and affects the direction or strength of the diet effect. For example, the change in choline status score in responding to dietary choline may be observed in subjects with one genotype (responders), but not in subjects with other genotypes (non-responders). The genotypes that modify the diet effect will be identified by the diet \times genotype interaction term. This analysis will be performed in the MIXED procedure in SAS (SAS Institute, Inc., Cary, NC). Benjamini-Hochberg method for False Discovery Rate (FDR) correction will be used for multiple testing correction. To improve the normality of the data, data transformation such as log transformation will be applied to metabolomics data, and outliers with studentized residue > 3 or < -3 will be excluded. Post hoc comparisons will be performed to identify metabolites associated with different levels of dietary choline and different genotypes. The analysis described above will also be applied to choline pool size data to identify significant diet \times genotype interaction effect for choline pool size.

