6.4 Sample Size and Power

Sample size estimation (Aim 1, SubAim 1a,1b). Similar to OPLS-DA, OPLS-R is a multivariate method for prediction. Different from hypothesis testing methods such as t-test or ANOVA, where sample size is determined by the power of rejecting null hypotheses when the alternative hypothesis is true, the sample size of OPLS-R is determined by its accuracy of prediction. In this study, we propose to recruit three groups of subjects (healthy men, pre- and postmenopausal women) with $n=60$ /group (estimated that $n=50$ /group will complete study). We plan to analyze all three groups together ($n=50*3=150$ subjects) to identify a formula for composite score that can predict choline pool size for all three groups. In case the universal score does not perform well, we will analyze each group ($n=50$ subjects) separately. Using our previous data with $n=44$ subjects, we successfully identified a panel of metabolites that can be used to predict whether a sample is taken at baseline or after choline deficient diet. As shown by the ROC plot, the area under curve was 98.77%, which indicates very high sensitivity and specificity (Figure 2). Our previous study indicates that there is a strong association between the panel of biomarkers and choline status even when the model was developed with a relatively small number of samples.

Sample size estimation (SubAim 1c). This analysis will first be applied to the *PEMT* SNPs (rs12325817-C; rs4646343-A and rs3760188-A) that are known to interact with the effect of dietary choline in women but not in men (24). This analysis serves to confirm the consistency between the performance of the choline status score and existing knowledge. Assuming the effect size of the diet \times genotype interaction is 0.6 (moderate effect), we

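### SubAim 1c hypothesises a genotype difference in level at every intake, but the plan names and powers only the diet × genotype interaction, which is neither necessary nor sufficient for that hypothesis

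*Combined protocol and SAP*

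**What the plan says.** **The hypothesis.** Sections 2.2 and 6.2 (Secondary Endpoint) state that "people with these SNPs have a lower choline pool size/worse choline status score for any given choline dietary intake" than non-carriers. Section 5.1 (Genotyping) uses this as a validity check on the two measures: carriers should "have values for Cho score and isotope dilution that show that they have smaller pool size for any given diet treatment".

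**The model.** Section 6.3 lists its terms as "Diet effect (fixed), genotype effect (fixed), subject effect (random) and diet" × genotype. The response is the choline status score. The model is fitted separately in men, premenopausal women and postmenopausal women.

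**The inference.** For the score: "The genotypes that modify the diet effect will be identified by the diet" × genotype term. For pool size: "The analysis described above will also be applied to choline pool size data to identify significant diet" × genotype effect. The only other genotype comparison concerns metabolites: "Post hoc comparisons will be performed to identify metabolites associated with different levels of dietary choline and different genotypes". Section 6.3 also sets genotype aside as a confounder because each person acts as their own control.

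**The power.** Section 6.4 begins "Assuming the effect size of the diet" × genotype interaction is 0.6, and reports 89.61% at P<0.05. No power is given for a genotype difference in level.

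**The concern.** The hypothesis is about whether carriers sit lower than non-carriers at each intake. The named test asks whether the gap between them changes across intakes. Because SubAim 1c is the stated secondary endpoint and a check on the validity of the score and the isotope dilution measure, a mismatch can mislead in two ways. A sound score could appear to fail because the carrier deficit is similar on all diets. An unsound one could appear to pass because the gap changes sign across diets.

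There is also a pre-specification issue. The genotype term will be in the output with no stated role, so the choice between main effect and interaction could be made after seeing the results.

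**Working it through.** **1. Inputs.**
- From the documents: 50 completers per group, effect size 0.6, P<0.05 and 89.61% (section 6.4); 44% of premenopausal women unable to induce *PEMT* (section 5.1); 74% of Caucasian women with the rs12325817 C allele (section 1.1).
- Assumed, not in the documents: total SD of 1, equal correlation ρ between any two diets, ρ from 0.4 to 0.8, two-sided tests, and the patterns of deficit below.

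**2. The plan's own figure.** N, genotype split, sidedness, ρ and the scale of the 0.6 are not given with the 89.61%, so it cannot be reproduced uniquely. As a two-sided two-sample t-test with d = 0.6:
- 28/22: 54.1%
- 56/44 (100 women): 83.9%
- 67/53 (120 enrolled women): 89.9%
- 111/39 (all 150): 89.3%

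As an interaction contrast of 0.6 SD between the 100% and 25% diets with a 22/28 split, power is 54.1% at ρ = 0.5 and 90.4% at ρ = 0.8. On any of these readings, the document attaches its figure to the interaction only.

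**3. What each term tests.** Let δ be the carrier deficit at 100%, 50% and 25%.
- Hypothesis: all three δ are above zero.
- Genotype main effect: the mean of the three, δ̄.
- Interaction: whether the three are equal.

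**4. Formulas.**
- Main effect: a person's mean over three diets has variance (1 + 2ρ)/3, so the noncentrality is δ̄/√((1 + 2ρ)/3) × √(n₁n₂/N), with N − 2 df.
- Interaction: λ = (n₁n₂/N) × Σ(δ − δ̄)²/(1 − ρ), F with 2 and 2(N − 2) df.

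**5. One group of 50, split 22/28.** Here n₁n₂/N = 616/50 = 12.32, with square root 3.510.
- Main effect, δ̄ = 0.6: at ρ = 0.4, 0.6/0.775 × 3.510 = 2.72, power 0.76. At ρ = 0.8, 0.6/0.931 × 3.510 = 2.26, power 0.60.
- Interaction, 0.3/0.6/0.9: Σ = 0.18. At ρ = 0.4, λ = 12.32 × 0.18/0.6 = 3.70, power 0.38. At ρ = 0.8, λ = 11.09, power 0.84.

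| Deficit at 100/50/25% (SD) | Fits the hypothesis? | Interaction, ρ 0.4 → 0.8 | Main effect, ρ 0.4 → 0.8 |
|---|---|---|---|
| 0.6/0.6/0.6 | yes | 0.05 → 0.05 | 0.76 → 0.60 |
| 0.3/0.6/0.9 | yes | 0.38 → 0.84 | 0.76 → 0.60 |
| 0.1/0.4/0.9 | yes | 0.62 → 0.98 | 0.54 → 0.41 |
| −0.3/0/0.3 | no | 0.38 → 0.84 | 0.05 → 0.05 |

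The second and fourth rows have the same Σ, so the interaction test cannot tell them apart, although one satisfies the hypothesis and the other contradicts it.

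**6. A less even split.** With 37/13 (74%), √(481/50) = 3.102. Main-effect power for 0.6 SD is 0.65 at ρ = 0.4 and 0.50 at ρ = 0.8.

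**7. A contrast at a single diet.** For 0.6 SD with 22/28, the noncentrality is 0.6 × 3.510 = 2.11 and power is 54.1%. Per-diet contrasts are therefore better shown with intervals than each required to be significant.

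**The case against.** A reader might infer that the interaction is zero whenever the hypothesis is true, so that the planned test must fail. The documents do not support that. A deficit at any given intake fixes its direction at each diet, not an equal size. The synopsis (Efficacy Evaluations) expects genotype to change the rate at which diet alters pool size, section 5.1 expects some women to deplete more slowly, and section 6.4 describes the *PEMT* SNPs as already known to interact with dietary choline in women. Under such patterns the interaction has real power, and in the third row of the table it beats the main effect. Nor does any passage say that the deficit would show mainly as a constant shift.

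It would also be wrong to say that the model omits the level effect. Genotype is a fixed term and can be estimated. The section 6.3 sentence on the interaction is limited to genotypes that modify the diet effect, and for those it is the right test. It also suits the *PEMT* consistency check in section 6.4, and the power figure is openly labelled as interaction power. The scan of more than 2 million SNPs is declared exploratory.

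All of this stands. It narrows the point without removing it: no test, contrast, decision rule or power is stated for the level difference in score or pool size that the secondary endpoint hypothesises.

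**Conclusion.** The concern holds as a gap between hypothesis and test for the secondary endpoint. A significant interaction is neither necessary for the hypothesis (constant deficit: 5% rejection, whatever the SD, correlation or split) nor sufficient (crossing pattern). How much is lost depends on how the deficit varies across diets, which the documents do not state. At n = 50 and a 22/28 split, interaction power runs from 0.05 to 0.98 over the three patterns that satisfy the hypothesis. Main-effect power over the same patterns runs from 0.41 to 0.76. Neither test dominates, so the level contrast belongs beside the interaction and should not replace it. Apart from the 5% result, these figures rest on the assumed SD, correlation and deficit patterns and are illustrative.

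**What to change.** **Section 6.3.** Name the genotype main effect, averaged over the three diets, as the test of the section 6.2 hypothesis for both score and pool size. Report the genotype contrast at each diet with its confidence interval, so that the direction at every intake can be seen. Keep diet × genotype as the test of effect modification and of the known *PEMT* interaction.

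Do not extend the own-control argument to the genotype contrast. Genotype varies between persons, section 3.4 describes a recruitment area of mixed ancestry, and section 6.3 lists no covariates. Adjust for ancestry using the array data in section 5.1. Section 10 defers genotyping to a later date, so this adjustment depends on the array being run.

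**Section 6.4.** State that 89.61% applies to the interaction only, and give its N, genotype split, sidedness, correlation and the scale of the 0.6. Add power for the genotype contrast with the same inputs. On the assumptions above, for 0.6 SD in one group of 50, it is about 0.60–0.76 at a 44/56 split and 0.50–0.65 at 74/26.

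**Cost.** The model keeps its terms apart from the ancestry adjustment, and no new data or participants are needed. The level contrast adds one test per SNP within the planned false discovery rate correction. On these assumptions its stated power in a single group of 50 will be visibly below 89.61%.

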will have 89.61% of power to detect it at $P<0.05$ cutoff. The same analysis will then be performed for all other SNPs (>2 million) measured in this study. We will be under-powered for the global analysis after multiple testing adjustment for 2 million tests, so this analysis will be an exploratory analysis. To increase statistical power, we will use SNP based pathway enrichment analysis method (102). This analysis was developed for GWA studies, and addresses the lack of power issue in GWA studies. It will identify SNPs with jointly significant genetic effect, i.e. sharing the same biological pathways, even when the individual P value for each SNP may not be significant. The pathways identified from this analysis may provide insight into the regulation of choline metabolism.

7 STUDY INTERVENTION (drug, device or other intervention details)

Diets: The experimental diets, delivering 100%, 50% and 25% of the recommended intake of Cho (in all forms) (550 mg Cho/70 kg body weight/d), are identical except for the bread that we offer (Cho in the bread will be varied to deliver the desired Cho above that delivered by the base Cho diet as described previously (1)). The base Cho diet is composed of 0.8 g high biologic value protein/kg [current Recommended Dietary Allowance (RDA)], with 30% kcal coming from fat and the remaining kcal from carbohydrate; diets are prepared in-house to protocol specifications and are similar to those described in detail in a publication in JADA (1). These diets were designed to bracket the range of dietary intake observed in several large published human population studies (18-23, 75). We have experience using these limited Choline level diets for more than 60 days per subject in our previously published studies (10, 24, 25, 51, 55).

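### Excluding observations with studentized residuals beyond ±3 makes the SubAim 1c diet × genotype P values modestly too small, and no analysis of all observations is planned

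*Combined protocol and SAP*

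**What the plan says.** All references are to the combined protocol and SAP.

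- **Model (6.3).** SubAim 1c uses a repeated-measures linear model with diet, genotype and their interaction as fixed effects and subject as random. "This analysis will be performed in the MIXED procedure in SAS". For the response, "the choline status score defined by Aim 1 is the response variable"; the same analysis is also applied to choline pool size.
- **Analysis sets (6.3, 6.4).** "This analysis will be performed for each diet period (healthy men, pre- and postmenopausal women) separately", which I read as one model per group of men, premenopausal and postmenopausal women, with "estimated that $n=50$ /group will complete study".
- **Exclusion (6.3).** In a sentence that begins with transforming metabolomics data to improve normality, "outliers with studentized residue > 3 or < -3 will be excluded". The plan does not say which residual is meant (conditional or marginal, internally or externally studentized), whether the rule is repeated after refitting, or whether the observation or the whole subject is dropped.
- **Use (6.3, 6.4).** The three PEMT SNPs are tested first, to confirm the score against existing knowledge, at P<0.05. Then "The same analysis will then be performed for all other SNPs", more than 2 million of them; this part is called exploratory. P values go into a Benjamini-Hochberg correction and a pathway enrichment analysis.

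**The concern.** The rule removes points because the fitted model explains them badly, then tests the remainder as if it were the full sample. The residual variance shrinks by more than the loss of data justifies, so standard errors and P values come out too small. This happens without any true outlier: a normal sample always has some residuals beyond 3.

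Two things are at stake. The first is the error rate of the diet × genotype tests, both for the PEMT SNPs and at the small P values that drive the FDR and pathway results. The second is that some large residuals may be real responses. SubAim 1c looks for people whose response to dietary choline differs, and no planned analysis would show what the exclusion had removed.

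**Working it through.** **The plan's own figure.** For SubAim 1c the plan states only a power: it "will have 89.61% of power to detect it at $P<0.05$ cutoff", for an interaction effect size of 0.6. It cannot be reproduced, because the sample size, genotype split, sidedness and test are not given for that calculation. For example, 100 women split 56/44 give 0.6/√(1/56 + 1/44) = 2.978, and 2.978 − 1.960 = 1.018, a power of 84.6%. Nothing below depends on this figure. The plan states no error rate after exclusion.

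**Inputs.** From the plan: 50 completers per group × 3 diets = 150 observations per model, and a cutoff of ±3. From Section 5.1: 44% of premenopausal women cannot induce PEMT, so 22 v 28 of 50. Assumed: single observations are deleted once and the model is refitted; within-subject correlation 0.5, with 0.2 (marginal residuals only) and 0.8 as the range.

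**How often the rule acts.** In normal data, P(|Z|>3) = 0.0027, so 150 × 0.0027 = 0.40 deletions are expected per model. Simulation gave 0.33 to 0.37, with at least one deletion in about 30% to 33% of models.

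**Large-sample formula.** Let c = P(|Z|≤3) = 0.9973, k = 6φ(3) = 0.0266 and m = c − k = 0.9707. After one pass of deletion around the fitted mean:

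- true variance of the mean (× n) = [m(1 + 2k) + k²]/c² = 1.0286
- variance the analysis reports (× n) = (m/c)/c = 0.9760
- the test statistic is inflated by √(1.0286/0.9760) = 1.027

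So 1.960/1.027 = 1.909, and 0.05 becomes 0.056. Likewise 0.01 becomes 0.0121, 0.001 becomes 0.00135, and 5×10⁻⁸ becomes 1.1×10⁻⁷ (2.2-fold).

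**Simulation of the planned model.** Random-intercept REML fit, normal data, no effects, two-degree-of-freedom interaction test at 5%:

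| Residual | Correlation | Data sets | No deletion | After deletion | Paired excess, points (SE) |
|---|---|---|---|---|---|
| Conditional | 0.5 | 8,000 | 5.09% | 6.02% | 0.94 (0.13) |
| Conditional | 0.8 | 4,000 | 5.00% | 6.35% | 1.35 (0.21) |
| Marginal | 0.2 | 6,000 | 5.17% | 5.85% | 0.68 (0.15) |
| Marginal | 0.5 | 8,000 | 5.29% | 5.70% | 0.41 (0.11) |
| Marginal | 0.8 | 4,000 | 5.50% | 5.83% | 0.32 (0.13) |

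A purely within-subject interaction model of the same size goes from 5.0% to between 6.1% and 6.6%. The genotype main effect rises by 0.10 to 0.50 points; at correlation 0.8 with conditional residuals, the rise of 0.10 (SE 0.10) cannot be told from zero.

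**Small P values.** At the 1% level with conditional residuals and correlation 0.5, 0.99% becomes 1.44%. A simpler two-group contrast (22 v 28) allows far more replicates:

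| Nominal level | Externally studentized | Internally studentized |
|---|---|---|
| 5% | 6.0% | 5.5% |
| 0.1% | 0.18% | 0.14% |
| 0.01% | 0.024% to 0.026% | 0.017% to 0.019% |

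The within-subject model gives about 2-fold at 0.001. With marginal residuals the growth is not established: at the 1% level and correlation 0.5 the excess is 0.06 points (SE 0.04).

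**Real responders (assumed scenarios, 400 data sets each, response on the 25% diet).**

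- 4 of 22 carriers shift by 3 SD: 32% of their responding observations are deleted, and interaction power falls from 28% to 17%.
- 4 of 22 shift by 4 SD: 61% are deleted, and power falls from 42% to 11%.
- 2 carriers shift by 4 SD: 89% are deleted.
- All carriers shift alike: 0.3% to 0.4% are deleted, close to the background rate.

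**The case against.** **Scope.** The sentence starts with metabolomics data, and the next one concerns metabolites associated with diet and genotype, so the rule may be meant for metabolite-level analyses only. That reading is possible. But a studentized residual exists only after a model has been fitted, the models in this paragraph have the score or pool size as response, and the score is built from those metabolites. The scope is open and should be stated.

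**Responders.** A reader might infer that the rule deletes the very responders that SubAim 1c is looking for. The documents do not support that. Section 6.3 describes responders as subjects sharing a genotype, and the diet × genotype term fits a shared shift, as the last scenario shows. Loss needs a strongly responding minority within a genotype, or response through a SNP that is not in the model. The second is plausible, since Section 1.1 lists several SNPs that alter the requirement while each model carries one genotype, but the sizes used here are assumptions.

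**SNP by SNP.** A reader might also infer that a different subset is dropped for each of the 2 million tests. That would follow from applying the rule within each model, but the plan does not say so.

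**Size and consequence.** The excess depends on an undefined residual, SubAim 1c is the secondary endpoint, and the genome-wide scan is declared exploratory. All of this stands and limits the weight of the point. The PEMT tests are nevertheless meant to confirm the score.

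**Cost of keeping everything.** With heavy tails, deletion buys power. For a shift of 0.6 with t errors on 4 degrees of freedom, keeping all data gives 57% against 67%. Part of that gap is the raised error rate: under such errors deletion removes 1.7% of the data and the 5% test rejects 6.3% of the time. After adjusting for size, the comparison is about 59% against 63%, a real but small loss.

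**Conclusion.** Wrong as written, small in magnitude. If the rule is followed in the SubAim 1c models, the diet × genotype tests reject about 5.5% to 6.6% of the time at a nominal 5%. The paired excess over keeping all data in the planned model is about 0.3 to 1.4 points; the smallest value, added to an exact 5%, would be 5.3%. The relative excess reaches roughly 1.4- to 2.4-fold between the 0.001 and 0.0001 levels, a range that rests on the large-sample formula, the two-group contrast and the within-subject model.

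These figures assume normal data, deletion of single observations in one pass, 50 subjects on three diets, and within-subject correlations of 0.2 to 0.8. They do not support a claim that every genotype test is seriously distorted, since the main effect moves by at most 0.5 points. Removal of true responders is a possibility under stated scenarios, not an expected result of the plan.

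**What to change.** - Make the analysis of all observations primary for SubAim 1c: the PEMT tests, pool size and the exploratory scan.
- Exclude a value only for a documented assay or sample fault, decided blind to diet and genotype.
- Keep the planned transformation (log, or rank-normal) as the means of handling heavy tails.
- State which data and models the ±3 rule covers, which residual is used, whether the rule is repeated, and whether an observation or a subject is dropped.
- Report the ±3 exclusion as a sensitivity analysis, with the number of observations removed by diet and genotype.

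The cost is SAP wording and one extra run, with no change to data collection. The price is slightly wider intervals, and a few points of power if tails remain heavy after transformation.
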